NMSC	France: treatment proxy if relevant	
	Only incident primary malignancies will be considered	
NMSC	ICD-10 codes† C44	Safety event of
		interest/endpoint

# Table 1. Preliminary Operational Definitions of the Main Study Variables

Variable	Definition for all countries unless otherwise	Role in the analysis
	specified	
MACE (22)	Definition for all countries unless otherwisespecifiedICD-10 codes† I20, I21, I60, I50, I11.0, I13.0, I13.2,I61, I62, I63, I64, H34Denmark and Sweden: Nordic Medico-StatisticalCommittee (NOMESCO) codes for coronary arterybypass graft (CABG) or percutaneous intervention(PCI):FNF, FNG, FNA, FNB, FNC, FND, FNEICD-10 codes I00-I99 as the underlying cause of deathin death certificates (cause of death registries)Due to longer lags for death certificate data, CV deathmay be defined based on death within 30 days of agiven diagnosis.France: CCAM procedure codes:For CABG: DDMA030, DDMA031, DDMA032,DDMA033, DDMA034, DDMA035, DDMA036,DDMA037, DDMA038, EPFA006, ENFA003For PCI: DDAF001, DDAF002, DDAF003,DDAF004, DDAF005, DDAF006, DDAF007,	Safety event of interest/endpoint
	DDAF008, DDAF009, DDAF010, DDAA002, DDFF001, DDFF002, DDLF001, DDPF002, DDSF001, YYYY082	
Bone fractures	ICD-10 codes M48.4, M48.5, M80, M84.3, M84.4, S02, S12, S22, S32, S42, S52, S62, S72, S82, S92, T02, T08, T10, T12, T14.2 (26). Additionally, surgery codes may be considered	Safety event of interest/endpoint
Neurological events of in	terest	
Peripheral neuropathy	ICD-10 codes: G60-G64, M54.1, G90.0	Safety event of interest/endpoint
Sensorineural hearing	ICD-10 codes: H90.3-H90.8, associated health services	Safety event of
loss	and devises may be considered	interest/endpoint
Migraine	ICD-10 codes: G43	Safety event of interest/endpoint
Seizures and seizure disorders	ICD-10 codes: G40, G41, P90, R56	Safety event of interest/endpoint
Demyelinating disorders including multiple sclerosis	ICD-10 codes: G35-G37	Safety event of interest/endpoint
Neurodegenerative disorders: Alzheimer, Parkinson, amyotrophic lateral sclerosis (ALS), spinal muscular atrophy (SMA), multiple system atrophy	ICD-10 codes: G12, G20, G23, G30	Safety event of interest/endpoint
Growth metrics conditional on sufficient data available beyond age 12 years	Denmark only: height and weight as recorded in the Danish Children's Database. Height and weight measures in adolescents will be benchmarked to geographically appropriate age and sex strata as percentiles in growth curves.	Safety event of interest/endpoint

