### 9.3.2. Endpoints

The following endpoints (safety events of interest) will be assessed.

- Thromboembolic events, including:
  - VTE (including deep vein thrombosis [DVT] and pulmonary embolism [PE])
  - Arterial thrombosis (includes myocardial infarction [MI] and stroke)
- HZ
- Serious infections
- Opportunistic infections
- Incident primary malignancy, including:
  - Incident primary malignancy excluding nonmelanoma skin cancer (NMSC), overall and by major organ
  - Incident NMSC
- MACE\*, including (22):
  - o Nonfatal MI
  - Nonfatal stroke
  - Unstable angina
  - Hospitalization due to heart failure
  - Coronary revascularization by percutaneous intervention or coronary artery bypass graft
  - Cardiovascular death
  - \*Other MACE definitions (eg, excluding unstable angina, hospitalized heart failure, revascularization procedure) may be considered.
- Neurological events of interest (including the following events that are captured in at least one of the databases):
  - Peripheral neuropathy
  - Sensorineural hearing loss
  - o Migraine
  - Seizures and seizure disorders
  - Demyelinating disorders including multiple sclerosis
  - Neurodegenerative disorders
- Bone fractures

PFIZER CONFIDENTIAL

CT24-WI-GL02-RF02 5.0 Non-Interventional Study Protocol Template For Secondary Data Collection Study 01-Aug-2023 Page 18 of 47

- Growth metrics in adolescents
  - height and weight, conditional on sufficient data available beyond age 12 years (Denmark only)

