### Table 1. Preliminary Operational Definitions of the Main Study Variables

CT24-WI-GL02-RF02 5.0 Non-Interventional Study Protocol Template For Secondary Data Collection Study 01-Aug-2023 Page 24 of 47

Variable	Definition for all countries unless otherwise specified	Role in the analysis
Cause-specific	As recorded in each database:	Safety event of
mortality (part of	The Danish Civil Registration System,	interest/endpoint
MACE)	The Danish Cause of Death Registry,	-
	The Swedish Cause of Death Register,	
	The French National Death Register (CepiDC)	

Table 1.	Preliminary O	perational Definitions	of the Main S	Study Variables
----------	---------------	------------------------	---------------	-----------------

\*Additional treatments may be defined in the SAP.

†Source of ICD-10 codes: France, inpatient hospital encounters; Denmark, Sweden, inpatient (hospital) or outpatient (specialist visits). ICD-10 codes with trailing letters are applicable in Denmark only.

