# Table 3.Age Standardized Incidence Rates (IRs) of Selected Safety Events of
Interest in Patients with Alopecia Areata (AA) in Denmark (Pfizer
data on file)

Event	IR per 1,000 PYs	PYs Needed to Observe Approximately 1 Event, Given Background IR	PYs Needed to Observe Approximately 1 Event, Given Doubling of Background IR
Any primary malignancy excluding NMSC a	1.13	885	442
Thromboembolic events	1.17	855	427
DVT	0.87	1,149	575
PE	1.09	917	459
ATE	2.50	400	200
MACE b	1.41	709	355
Herpes zoster infection	1.83	546	273
Serious infections c,d	1.89	529	265

a. Incidence rate of malignancy including NMSC in patients with AA not available.

b. Defined by the following outcomes: CV death; acute myocardial infarction; unstable angina; ischemic stroke; haemorrhagic stroke; hospitalization due to heart failure; coronary revascularization by percutaneous intervention or coronary artery bypass graft.

c. Including the following infection types: abscess, bacteraemia, candidiasis and other fungal infections, coronavirus disease of 2019 (COVID-19), female pelvic infections, heart infections (acute rheumatic fever, infectious peri- or myocarditis, endocarditis), human immunodeficiency virus disease, infections of central nervous system, infectious complications of procedures, catheters etc., influenza, intra-abdominal infections, male genital infection, miscellaneous bacterial infection, miscellaneous viral infections, obstetrical infections, other lower-respiratory tract infections, parasitic infections, pneumonia, sepsis, sexually transmitted diseases, skin infections, and viral hepatitis. d. Incidence rate of opportunistic infections in patients with AA not available.

Abbreviations: AA = alopecia areata; ATE = arterial thromboembolism; CV = cardiovascular; DVT = deep vein thrombosis; IR = incidence rate; NMSC = nonmelanoma skin cancer; MACE = major adverse cardiovascular event; PE = pulmonary embolism; PY(s) = person-year(s)

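### The preliminary Table 1 code list for MACE is broader than the MACE definition in section 9.3.2: all of I20, heart failure without an admission requirement in Denmark and Sweden, and H34

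*Protocol*

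**What the plan says.** Section 8.2 lists MACE among the primary safety events. Section 9.3.2 gives its components, which include "Unstable angina", "Hospitalization due to heart failure" and "Nonfatal stroke". No retinal vascular event is among them. The same section adds: "Other MACE definitions (eg, excluding unstable angina, hospitalized heart failure, revascularization procedure) may be considered".

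Footnote b to Table 3 (section 9.5) describes the MACE outcome behind the Danish background rate in much the same clinical terms: "acute myocardial infarction; unstable angina; ischemic stroke; haemorrhagic stroke; hospitalization due to heart failure", together with cardiovascular death and coronary revascularization.

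The MACE row of Table 1 (section 9.3.4) opens with "I20, I21, I60, I50, I11.0, I13.0", continues with I13.2 and the remaining stroke codes, and closes with H34. The list carries a dagger, which the table footnote explains as follows: "Source of ICD-10 codes: France, inpatient hospital encounters; Denmark, Sweden, inpatient (hospital) or outpatient (specialist visits". The row states no admission, overnight-stay or primary-diagnosis condition.

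Section 9.3.4 presents Table 1 as a starting point and leaves refined, country-specific definitions to the SAP.

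**The concern.** An endpoint defined in words in one section and in codes in another has to come out as the same endpoint. Here three parts of the code list go beyond the words. MACE is a primary safety event, and its incidence rate in each exposure cohort is a main result of the study.

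If the list were programmed as printed, the MACE count would include people whose first recorded event is angina other than unstable angina, heart failure seen only at a Danish or Swedish specialist clinic, or a retinal vascular occlusion. The reported rate would then describe something other than the endpoint in section 9.3.2. The heart failure component would also mean one thing in Denmark and Sweden and another in France, so part of any difference between countries would come from the definition.

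**Working it through.** The main check sets the endpoint definition beside the code list.

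1. **Angina.** Section 9.3.2 and Table 3 footnote b restrict this component to unstable angina. Table 1 gives I20 with no fourth character. In ICD-10, which the protocol adopts in section 9.3.4, unstable angina is I20.0 and the rest of I20 covers other and unspecified angina. That subcode content comes from the classification; the protocol does not spell it out. The row itself supports reading bare I20 as the full category, because it uses four-character codes where it wants a subset (I11.0, I13.0, I13.2).

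2. **Heart failure.** Section 9.3.2 and footnote b require a hospitalization. Table 1 lists I50, I11.0, I13.0 and I13.2 under the dagger, so an outpatient specialist contact qualifies in Denmark and Sweden, while only inpatient encounters qualify in France. This contradiction lies wholly within the protocol. It is not a habit of the table to leave care setting unstated: the serious infection row requires a primary diagnosis and at least one overnight stay.

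3. **H34.** This is the ICD-10 category for retinal vascular occlusions, both arterial and venous. Neither section 9.3.2 nor footnote b names a retinal event of either kind.

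The related figures in section 9.5 reproduce:

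- Person-years per MACE event at the background rate: 1,000 / 1.41 = 709.2 (stated 709).
- At double the rate: 1,000 / (2 × 1.41) = 354.6 (stated 355).
- Ritlecitinib person-years: 74×8 + 96×7 + 110×6 + 127×5 + 144×4 + 161×3 + 123×2 = 3,864, and 2 × 3,864 = 7,728 at 1:1 (both as stated).
- Expected MACE events over 7,728 person-years at the Table 3 rate: 7,728 × 1.41 / 1,000 = 10.9, over both groups and all three countries. The protocol does not print this figure.

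The calculation stops there. No rate is given for angina other than unstable angina, for heart failure managed in clinics, or for retinal occlusion, so neither the coded MACE rate nor the share of counted events outside the definition can be computed. The 10.9 shows only that the expected count is small before it is divided among countries.

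**The case against.** The strongest reply is that Table 1 is expressly preliminary. Section 9.3.4 says the SAP will hold refined definitions of all study variables, and section 9.3.2, which already has the right clinical wording, can be read as governing. The dagger footnote is a general statement of where codes come from and need not cancel the hospitalization condition. This lowers the severity. It does not remove the mismatch, because the protocol prints two definitions that do not agree and the MACE row gives a programmer no admission condition to apply. Section 9.7 also says that major changes to primary endpoint definitions would be reflected in a protocol amendment, which favours aligning the two early.

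Second, section 9.7.5 plans a re-analysis of MACE under an alternative definition, and the examples in section 9.3.2 drop unstable angina and hospitalized heart failure. Such a variant would remove most of points 1 and 2. But the choice of variant is open, the examples do not address H34, and a variant without these components does not supply the stated main definition.

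Third, results are analysed and reported by country, individual data are not pooled, and section 9.9 discloses that the French source lacks diagnoses outside inpatient stays. That limits the harm from the country difference. For heart failure, however, the difference is avoidable, because inpatient diagnoses exist in all three countries.

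Fourth, H34 follows the stroke codes in a row that cites a published source, and it may be intended. That is a fair point, and it is why deletion is only one of the two options below.

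A reader might also infer several stronger claims that the documents do not support:

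- **A stated degree of inflation or dilution.** If the added diagnoses numbered k per true MACE event and treatment had no effect on them, a true doubling would read as (2 + k)/(1 + k): 1.91 at k = 0.1 and 1.50 at k = 1. Nothing in the protocol fixes k or supports the no-effect assumption. The analysis counts first events after excluding prevalent cases (section 9.7.2), so repeat visits for established disease do not accumulate. Hazard ratios are exploratory in any case.
- **That 1.41 per 1,000 person-years was obtained with different codes.** Footnote b gives clinical names only. The codes and settings behind the rate are not shown and may or may not match Table 1.
- **That patients with stable angina or clinic-managed heart failure would be excluded as prevalent cases.** Section 9.7.2 does not say that the event code list defines prevalence.

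**Conclusion.** The point holds as a mismatch between the preliminary MACE code list and the protocol's own MACE definition, in three places: bare I20, the care setting of the heart failure codes in Denmark and Sweden, and H34. Applied as printed, the list would count first diagnoses outside the stated endpoint, and its heart failure component would differ between the Nordic countries and France.

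The size of the effect is unknown and cannot be derived from the documents. Whether the Table 3 benchmark is like for like is also unknown. The heart failure contradiction rests on the protocol alone. The points on I20 and H34 rest in addition on the content of those ICD-10 categories.

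Because Table 1 is labelled preliminary and an alternative MACE definition is planned as a sensitivity analysis, this is something that should be fixed. It does not invalidate the design.

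**What to change.** In the MACE row of Table 1:

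- Replace I20 with I20.0.
- Restrict I50, I11.0, I13.0 and I13.2 to inpatient admissions in all three countries. A primary-diagnosis condition is optional: it would reflect that the admission must be caused by heart failure, but neither section 9.3.2 nor footnote b demands it.
- Delete H34. If it is intended, name the retinal component in section 9.3.2 and list its subcodes.

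The SAP definitions should carry the same list. The change is an edit to a code list and needs no new data; data collection is not due to start until September 2027. The downside is fewer MACE events, by a number the documents do not allow one to estimate, for an endpoint where few are expected.

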# 8.2. Primary Objective

The primary objective is to estimate the IRs of safety events of interest among patients with AA initiating ritlecitinib and patients with AA initiating baricitinib or other approved systemic treatments for AA in a real-world setting. The following are the primary safety events of interest:

- Thromboembolic events (including VTE and arterial thrombosis)
- Herpes zoster (HZ)
- Serious infections
- Opportunistic infections
- Malignancy
  - Malignancy excluding nonmelanoma skin cancer (NMSC)
  - o NMSC
- Major cardiovascular event (MACE)
- Neurological events of interest
  - Peripheral neuropathy
  - Sensorineural hearing loss
  - o Migraine
  - o Seizures and seizure disorders
  - o Demyelinating disorders including multiple sclerosis
  - o Neurodegenerative disorders
- Bone fractures
- Growth metrics in adolescents (height and weight, conditional on sufficient data available beyond age 12 years; Denmark only)

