### 9.3.4. Preliminary Operational Definitions of the Main Study Variables

Generally, in the participating data sources, disease is identified by diagnoses recorded at hospitalizations (all three countries) or at hospital-based specialist outpatient clinics (Denmark and Sweden). Diagnoses are currently coded using the World Health Organization (WHO) International Classification of Diseases, Tenth Revision (ICD-10). The Danish version of the ICD-10 may have more detailed codes compared with the WHO ICD-10. ICD-11 will be used if introduced during the study period. Treatment records originate, depending on the database, from outpatient dispensings, from hospital administrations, and are coded using the Anatomical Therapeutic Chemical (ATC) classification or local structured vocabularies (e.g., local treatment codes in Denmark).

Table 1 summarizes the initial operational definitions of the eligibility criteria, the exposure and the endpoints. The refined, country-specific definitions of all study variables as well as the final list of other variables with their operational definitions will be provided in the SAP.

Variable	Definition for all countries unless otherwise	Role in the analysis
	specified	
Age	In years	Eligibility criterion,
		demographic characteristic
Sex	Male, female, other	Demographic
		characteristic
Ritlecitinib	ATC code L04AF08	Exposure
Baricitinib*	ATC code L04AA37 (through 2023) L04AF02 (2024	Exposure
	onwards)	
	Treatment code BWHP106 (Denmark only)	
AA	ICD-10 code † L63	Eligibility criterion
Thromboembolic events	ICD-10 codes † I26, I260A I269A, I67.6, I74, I80.1,	Safety event of
(including DVT, PE,	180.2, 181, 182.0, 182.2; 182.3, 182.8, 182.9 022.3,	interest/endpoint
and arterial thrombosis)	087.0, 087.1, 0882D, 0882E, T817D	
HZ	ICD-10 codes † B01, B02, H031F, H131M, G051M,	Safety event of
	H190D, H192D, H190J, H220C, B027, B028, B029,	interest/endpoint
	G0511, H621B	
	ATC codes J05AB01 (HZ-specific tablet dose 800 mg	
	in package of 35 tablets based on product code)	
	J05AB11 (HZ-specific tablet dose: 500 mg based on	
	product code)	
	J05AB09 (HZ-specific tablet dose: 500 mg based on	
	product code) (23)	
Serious infection	ICD-10 codes† as the primary diagnosis at a hospital	Safety event of
	contact with a minimum of 1 overnight stay (24) A00-	interest/endpoint
	B99, D/3.3, E06.0, E32.1, G00-G02, G04.2, G05-G07,	
	H00.0, H44.0, H60.0-H60.3, H66-H67, H70, I30.1,	

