# 9.7.2. Analyses of the Primary Objectives

The primary analysis will comprise estimation of IRs with 95% CIs for the safety events of interest using a time-to-event analysis (except the growth metrics, which will be reported using means, medians or percentiles as appropriate). The analyses will include:

- Total number of patients in each exposure cohort
- Number of each new safety event of interest observed during the follow-up time in each exposure cohort
- Crude IRs (and cumulative incidences over selected prespecified periods) of the safety events of interest and 95% CIs in each exposure cohort
- Age- and sex-standardized IRs and 95% CIs in each exposure cohort

The summary of event rates will report time to first event since index date for each exposure cohort with appropriate censoring rules applied for those who do not experience an event by the end of the follow-up period, including those who die and those who emigrate. Rates will be expressed as events/10,000 person-years (PYs) of follow-up or a larger denominator if appropriate.

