### PFIZER CONFIDENTIAL

CT24-WI-GL02-RF02 5.0 Non-Interventional Study Protocol Template For Secondary Data Collection Study 01-Aug-2023 Page 30 of 47 The index date and follow-up period will be considered separately with respect to acute-onset outcomes (thromboembolic events, all infection endpoints, MACE) versus delayed outcomes (malignancy excluding NMSC, NMSC, fracture, the neurologic events of interest, MACE). IR and cumulative incidence of each endpoint will be computed after excluding patients with a respective prevalent condition. This lookback period to identify prevalent conditions may be shorter for acute-onset outcomes than for delayed outcomes. For events with long induction/latency period (e.g. malignancy, MACE), events during a prespecified post-index date period may be disregarded and considered prevalent, according to the hypothesized induction/latency periods. The endpoint MACE will be analysed using both approaches. Approaches with and without censoring at treatment discontinuation will be considered.

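### The primary safety event peripheral neuropathy counts M54.1 (radiculopathy) without a stated source or reason; the code should be moved out of the main definition

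*Protocol*

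**What the plan says.** Section 8.2 introduces its list with "The following are the primary safety events of interest", and "Peripheral neuropathy" appears there and again in Section 9.3.2 under the neurological events. Table 1 defines it by the ICD-10 codes "G60-G64, M54.1, G90.0". The row has no literature reference and no note on how the list was chosen. It also sets no requirement on diagnosis position or on a supporting diagnosis.

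The status of the table is stated in Section 9.3.4: "Table 1 summarizes the initial operational definitions of the eligibility criteria, the exposure and the endpoints". The same section leaves refined definitions for each country to the SAP. Section 9.7 says that a major change to the definition of a primary endpoint would be reflected in a protocol amendment.

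For the analysis, Section 9.7.2 states: "The primary analysis will comprise estimation of IRs with 95% CIs for the safety events of interest using a time-to-event analysis". On patients with an earlier diagnosis it states: "IR and cumulative incidence of each endpoint will be computed after excluding patients with a respective prevalent condition". Section 9.1.2 ends follow-up at the event of interest. Section 9.7.3 makes the HR comparison exploratory, for the final report only and dependent on study size.

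**The concern.** Every code in the row belongs to the nervous-system chapter except M54.1, which sits in the back-pain category of the musculoskeletal chapter. Elsewhere in Table 1, M codes are used where a musculoskeletal condition is meant, as in the fracture row. The other G-coded neurological rows (migraine, demyelinating disorders, neurodegenerative disorders) contain no M code.

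The row also does not read as a deliberately broad definition. It leaves out G50-G59, the G-chapter block for nerve, nerve-root and plexus disorders, yet takes in one root diagnosis from another chapter.

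At stake is whether the reported rate can be read as a rate of peripheral neuropathy. Nothing else in the plan would show the contribution of M54.1. Section 9.7.5 plans an alternative definition for MACE but none for neuropathy. The limitations in Section 9.9 discuss under-recording of neurological events, and the general remark there on outcome misclassification gives hospitalisation and dispensing proxies as its example, not a code list that is too wide.

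**Working it through.** **The plan's own figure.** There is none to reproduce. Table 3 gives background rates for selected events and includes no neurological event, and the study-size section states no detectable HR for neuropathy. What follows combines the plan's rules with an assumed range.

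**What the rules do with an M54.1 record**

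1. *Incidence rate (Section 9.7.2).* A first M54.1 record in follow-up counts as a neuropathy event.
2. *Follow-up (Sections 9.1.2 and 9.7.2).* Time runs to the first event, so an M54.1 record ends follow-up and a later true neuropathy in that patient is not counted.
3. *Prevalent cases (Section 9.7.2).* A patient with M54.1 in the lookback leaves the neuropathy risk set without having had a neuropathy.
4. *Country reporting (Sections 9.3.4 and 9.7).* Diagnoses come from hospitalisations in all three countries, and also from hospital-based specialist outpatient clinics in Denmark and Sweden. Results are reported by country, so the M54.1 share could differ between the country tables.

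**Size under an assumed range**

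Let k be the number of M54.1 events per true neuropathy event. The documents do not give k; 0.5, 1 and 2 are assumed. The formulas ignore the smaller effects of items 2 and 3.

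- Share of the endpoint that is M54.1: k/(1+k).
- Inflation of the rate: 1+k.
- HR observed when the true neuropathy HR is 2, M54.1 is unrelated to treatment, and k refers to the comparator cohort: (2+k)/(1+k).

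| k (assumed) | Share M54.1 | Rate inflated by | True HR of 2 reads as |
|---|---|---|---|
| 0.5 | 0.5/1.5 = 33% | 1.5 | 2.5/1.5 = 1.67 |
| 1 | 1/2 = 50% | 2 | 3/2 = 1.50 |
| 2 | 2/3 = 67% | 3 | 4/3 = 1.33 |

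**What this does to the exploratory comparison.** The Schoenfeld formula (two-sided 5%, 80% power, 1:1, all assumed) gives events = 4 × (1.96 + 0.84)² / (ln HR)². The same formula approximately reproduces the plan's minimum detectable HRs: 6.66, 6.45 and 4.33, against 6.7, 6.4 and 4.3 stated in Section 9.5. At HR 2 it requires 66 events, and at HR 1.50 it requires 191.

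Adding M54.1 also adds events. With k = 1 and a true doubling, the two cohorts together have 2 + 3 = 5 events for every 1 + 2 = 3 without the code, a factor of 1.67. The requirement rises by 191/66 = 2.9, so on balance the comparison loses power.

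**The case against.** The strongest reply is that the definition is not final. Table 1 is headed as preliminary, Section 9.3.4 defers refined definitions of every variable to the SAP, and trimming a code list is ordinary SAP work. That limits the weight of the point but does not remove it. The code is stated in the protocol, not left open. The amendment rule in Section 9.7 makes this list the baseline for a primary event. Both infection rows carry a specific note on refining codes; this row does not.

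A second reply is that a nerve root is a peripheral-nerve structure and that safety surveillance may prefer a sensitive list. That would be defensible if stated. A list that takes one root code and omits G50-G59 does not look like that choice, and no reason is given.

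Third, the meaning of M54.1 is not written in the protocol. This is true, but it is part of the coding system that the protocol adopts.

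Fourth, excluding prevalent cases also removes some recurrent back disease and so limits the contamination. This stands as a partial offset, at the price of losing patients who are at risk of neuropathy.

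Three stronger readings are tempting and are not supported:

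- A reader might infer that the reported rate would be mostly back disease. No M54.1 share is given, and in the assumed range only k = 2 yields a majority.
- A reader might infer that the primary analysis is diluted. The primary objective estimates a rate per cohort, where the effect is inflation; movement toward 1 concerns only the exploratory HR.
- A reader might want G60 removed as hereditary disease. That ICD-10 category also covers idiopathic neuropathy, where a new case without a recognised cause could be coded.

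**Conclusion.** The point holds in limited form. A primary safety event includes one unexplained code for a different condition, and the plan's own rules carry that code into the numerator, the end of follow-up and the prevalent-case exclusion. The direct effect is a neuropathy rate that is too high by an unknown amount: 1.5 to 3 times over the assumed range of k.

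The effect on the exploratory HR, a true doubling read as 1.67 to 1.33, needs two further conditions: that the comparison is carried out at all, and that M54.1 events are unrelated to treatment. The documents establish neither. The conclusion about the code itself rests only on the Table 1 row and the standard ICD-10 meaning of M54.1.

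**What to change.** Remove M54.1 from the main definition of peripheral neuropathy and from the lookback that identifies prevalent neuropathy. Then either report radiculopathy as a separate line, or give the endpoint including M54.1 as a sensitivity analysis. Keep G60. Add a source or a one-sentence rationale to the row.

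The change is a code-list edit that needs no new data and can be made before extraction starts in September 2027 (Section 6). The cost is fewer events in the endpoint, hence a wider confidence interval relative to the rate, and one extra output line. If the sponsor wants root disease in the main definition, the protocol should say so, give the reason, and show the rate with and without M54.1.

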# 9.7. Data Analysis

Detailed methodology for summary and statistical analyses of data collected in this study will be documented in a SAP, which will be dated, filed, and maintained by the sponsor. The SAP may modify the plans outlined in the protocol; any major modifications of primary endpoint definitions or their analyses would be reflected in a protocol amendment. Data will be analysed and reported separately in each country. If relevant, meta-analysis of countryspecific results for the exploratory objective may be considered.

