# 9.9. Limitations of the Research Methods

The following are the potential limitations of this study:

- Unknown completeness of indication, as inferred from prior diagnoses, may lead to
  misclassified identification of the indicated population of patients dispensed ritlecitinib,
  baricitinib or other systemic AA treatment, by both incomplete capture of the indication
  of interest (AA) and incomplete exclusion of alternative on-label indications unless
  recorded at hospital encounters. In Denmark, indication may be recorded in a dispensing
  record in the Prescription Registry (estimated 82%). Correctness of this indication is
  close to 100% when compared against corresponding pharmacy records, however,
  validity against the clinical record has not been assessed (21). Reliance on hospital
  diagnoses to ascertain AA and other indications may lead to selection bias if unidentified
  patients with specific conditions differ systematically from those who are identified (54).
- The study will utilise data on dispensing or another administrative treatment record as a measure for intake of the drug. Relying on such records may lead to misclassification of the timing and status of exposure.
- Given the use of data sources from 3 distinct EU countries in this study, there will be variability in the type and completeness of the data captured across the data sources.
- Certain types of variables, such as anthropometrics and lifestyle (smoking, alcohol consumption, weight, height) are either not captured or are incomplete or have unknown completeness in some or all participating data sources. Completeness of recording of lifestyle factors, specifically smoking and alcohol use, is low, and the available proxies identify only persons with sequelae indicative of poor lifestyle. These proxies may also identify persons without a poor lifestyle.
- Several neurological safety events of interest are expected to be underrecorded in hospital encounters (eg, dizziness, headache). Therefore, the analysis is limited to endpoints that are well-captured by the data sources (eg, seizures).
- Some conditions including sensorineural hearing loss, and others that are primarily treated outside settings that contribute to the data sources, are likely to be under recorded

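### The preliminary code list for sensorineural hearing loss omits ICD-10 H91.0 (ototoxic) and H91.2 (sudden idiopathic), so patients with only those codes count as event-free

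*Protocol*

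**What the plan says.** Section 8.2 names sensorineural hearing loss among the primary safety events, and Section 9.3.2 lists it under the neurological endpoints ("Sensorineural hearing loss"). The Table 1 row reads "H90.3-H90.8, associated health services", followed by "and devises may be considered". The only flexibility in that row concerns services and devices, not further diagnosis codes.

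Section 9.3.4 gives the status of the table: "Table 1 summarizes the initial operational definitions of the eligibility criteria, the exposure and the endpoints". It then names the SAP as the place where the definitions become final: "The refined, country-specific definitions of all study variables as well as the final list of other variables with their operational definitions will be provided". Section 9.7 limits how far the SAP may go alone, since "any major modifications of primary endpoint definitions or their analyses would be reflected in a protocol amendment".

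Section 9.9 expects under-recording in hospital encounters for "Some conditions including sensorineural hearing loss, and others that are primarily treated outside settings that contribute to the data sources". It attributes this to where patients are treated and does not mention the code range.

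**The concern.** The endpoint is meant to pick up hearing loss as a possible adverse effect of a drug. The listed range includes mixed conductive and sensorineural loss (H90.6-H90.8), which is reasonable because mixed loss has a sensorineural component. It stops short of the codes for drug-attributed loss (H91.0) and sudden idiopathic loss (H91.2).

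The primary objective is the absolute incidence rate in each cohort, and a missing code lowers that rate whatever happens in the comparator cohort. The omission is also a separate cause of under-capture from the one disclosed in Section 9.9, and it is avoidable. In France, diagnosis codes come only from inpatient stays (Table 1 footnote and Section 9.9), so the choice of codes carries much of the ascertainment there.

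**Working it through.** The protocol gives no figure to reproduce: Table 3 has no background rate for hearing loss, and no section gives a split by code. The check is therefore a reading of the rule, plus a simple expression for its effect.

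**Inputs**
- Listed codes: H90.3-H90.8 (Table 1).
- H91 codes in the protocol: none.
- Coding system: WHO ICD-10 (Section 9.3.4). The meanings of H91.0 and H91.2 come from that classification; the protocol does not print them.
- Prevalent cases are excluded before each rate is computed (Section 9.7.2), and hearing loss is also a history variable (Section 9.3.3).
- Planned ritlecitinib follow-up: at most 3,864 person-years over all three countries, assuming no loss to follow-up (Section 9.5). Results are reported by country (Section 9.7), with counts of 1 to 4 masked (Section 9.10).

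**Applying the list as written**
1. Only H91.0 or only H91.2 recorded in follow-up: no event.
2. H91.0 or H91.2 first, then a code in H90.3-H90.8: an event, but dated late. Such cases are not lost.
3. H91.0 or H91.2 before the index date, with the same list used for lookback: not recognised as prevalent. A later H90.3-H90.8 code then counts as new. This works against the understatement, in a probably small group.

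**Effect on the incidence rate.** Let f be the share of wider-list cases that are coded only under H91.0 or H91.2. With rare events, person-time hardly changes. Leaving step 3 aside:

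captured rate = (1-f) × wider-list rate

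| f (assumed, not in the documents) | captured rate / wider-list rate |
|---|---|
| 5% | 1 - 0.05 = 0.95 |
| 10% | 1 - 0.10 = 0.90 |
| 30% | 1 - 0.30 = 0.70 |

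**Effect on the exploratory hazard ratio.** The ratio is multiplied by about (1-f in ritlecitinib) / (1-f in comparator). With 10% in both cohorts this is 0.90/0.90 = 1, so events are lost but there is no bias. Only unequal shares move it: 30% against 10% would give 0.70/0.90 = 0.78. Nothing in the documents indicates that the shares differ.

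**Effect on reporting.** A country-level count of five that loses one event becomes four and is masked under Section 9.10. With few person-years per country, a single event can matter in this way.

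**The case against.** The strongest reply is that the list is declared unfinished. Table 1 is titled preliminary, Section 9.3.4 sends refined definitions of every variable to the SAP, and the SAP is not at hand. The row also allows for services and devices, Section 9.4.1 names a Danish register that may be used to find hearing-related procedures and referrals, and Section 9.9 mentions treatment proxies. Much of this stands. It rules out calling the row a fixed error or a contradiction, and it lowers the priority. It does not add the codes. The two infection rows carry their own notes that the code lists will be refined, and this row does not. Section 9.9 itself doubts whether proxies can compensate.

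A second objection is that H91.0 requires a clinician to attribute the loss to a drug. Such coding may be readier for a new product under heightened monitoring, which Section 7 reports for ritlecitinib in Denmark, so adding the code could bring differential ascertainment. This is a fair point and the reason for reporting the two codes separately.

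A reader might also infer more than the documents support:
- That the omitted forms are those most relevant to an effect of ritlecitinib. The protocol ranks no subtype and describes no mechanism for hearing loss.
- That sensitivity to a true effect is close to zero. This needs the further assumption that any effect appears only under these two codes.
- That Section 9.9 predicts under-recording of slowly developing loss in particular. It makes no such distinction.

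**Conclusion.** The point holds as a minor one. As Table 1 stands, patients coded only H91.0 or H91.2 are counted as event-free. If the same list serves for lookback, they also go unrecognised as prevalent. The incidence rate is understated by the share f, apart from the small opposite effect of missed prevalent cases. The documents do not allow f to be estimated, and the 5%, 10% and 30% above are illustrations only. If f is equal across cohorts, the hazard ratio is roughly unchanged and only precision suffers.

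The conclusion rests on the standard WHO ICD-10 meanings of the two codes and on the SAP not already including them, which cannot be checked here. It shows an incomplete preliminary list, not an internal contradiction and not a demonstrated loss of signal.

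**What to change.** - Add H91.0 and H91.2 to the sensorineural hearing loss row of Table 1. If the omission is deliberate, state the reason there.
- Carry the same list into the SAP for the outcome, the exclusion of prevalent cases and the history variable.
- Report H91.0 and H91.2 also as a separate component, so that any difference in drug attribution between cohorts is visible.
- Settle this before the SAP is final, so that no question arises under Section 9.7 whether adding codes to a primary endpoint is a major modification.

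The cost is a code-list edit and one extra output row. The component will often fall in the masked range of 1 to 4. Showing the total and the component, without the remaining H90 count, avoids the total having to be masked as well under Section 9.10. The remaining downside is possible differential use of H91.0, which the separate row exposes but does not remove.
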